Study Design and Protocol

An Evaluation of a Milk-Based Nutritional Supplement to Effect a Positive Change in Bone Health in Post-Menopausal Women at Risk of Osteoporosis.

In a novel approach to the timing of nutrient ingestion, the proposed nutrient intervention seeks to modify (reduce) the rate of bone resorption and promote the rate of bone formation to the benefit of bone health in this at risk population.

2. Study design: A block randomised, cross-over design of 24h rates of bone turnover in healthy, post-menopausal women with osteopenia receiving either a milk-based protein supplement (MBPS) or isoenergetic (maltodextran) placebo control (PLACEBO).

3. Procedures:

Subjects: Post-menopausal women with osteopenia as determined by site-specific BMD (DXA) diagnosed and screened by a clinician ([name]) and for dietary intake of calcium and Vit D by a clinical dietitian ([name]).

Subject screening (clinical examination, 1h) and dietary intake of calcium and Vit D (by food frequency questionnaire, 1h) will precede the experimental protocol.

Experimental protocol and data collection: Supplemenary Material contains a Flowchart Subjects will attend for a 2 day overnight residence in the National Altitude Training Centre, Kilmurray Village. This facility is equipped to conduct residential human trials and has on-site individual bedroom accommodation subjects & researchers, a living room with fully equipped kitchen and laboratory to handle human blood samples.

The subjects' programmed protocol is as follows;

- 1. Arrive @ 17:00h with overnight bag;
- 2. Empty bladder and then provide and retain urine samples for the duration of the stay (assisted collection by researchers);
- 3. Consume a standardised evening meal (pre-prepared by the research dietitian) and then relax reading/watching films etc in the living room;
- 4. At 20:00h a research nurse will insert a cannula into a superficial arm vein and a blood draw (5ml) will be taken and processed for later analysis;
- 5. Further blood draws (5ml) will be taken at 22:00h, 2300h, 2400h,0100h and 0200h and the cannula withdrawn;
- 6. At 22:00h consume *either* maltodetran control (**PLACEBO**) (day 1) OR supplement (**MBPM**)(day 2) or *vice versa*;
- 7. Retire to bedroom;
- 8. Consume a standardised breakfast and lunch (pre-prepared by the research dietitian) whilst living in and around the University grounds (i.e. in close proximity to ensure 24h urine collection is complete);
- 9. Repeat from 2 above to end of 2nd day.

Total blood draw over 48h is $14 \times 5ml = 70ml$

[figure not shown]
- All formulations to be supplied food grade and product tested by Dairygold Coopertaive Society, Mitchelstown, Ireland.
- 4. Analytical methods:
- i. In total 224 (16 subjects * 7 samples * 2 d) blood samples will be collected. Separated aliquots will be frozen @ -80C and batch analysed for CTX (biomarker of resorption), P1NP (biomarker of formation). In total 32 (16 subjects * 2 d) 24h urine samples will be collected. Aliquots will be frozen @ -80C and batch analysed for uPYD, uDPD (biomarkers of resorption) normalised to urinary creatinine.

Ethical approval number: 2017_06_03_EHS

Date of Approval 26th June 2017

- ii. The I.O.F. recommended serum marker for bone resorption is CTX and formation P1NP. The magnitude and time course of the acute response (0-4h) change in bone turnover following ingestion of the MBPM vs. PLACEBO will be analysed by repeated measures ANOVA of the serum biomarkers of resorption and formation.
- iii. The overall influence on the diurnal change in bone turnover is best measured by a global biomarker of bone resorption specific to the type I collagen in bone. This is provided by the measurement of 24h urinary pyridinoline (PYD) and deoxypyridinoline (DPD) excretion normalised for urinary creatinine. Thus, the magnitude of effect of 24h change in bone resorption following ingestion of the MBPM vs. PLACEBO will be analysed by ANOVA(R) of the urinary markers of bone resorption (PYD/creatinine and DPD/creatinine).

Schematic Flow Chart of the Trial

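### As the steps are written, each 24h urine pool opens 2–5 h before the 22:00 product, so it misses the last 2–5 h after ingestion and, in period 2, includes the final hours of product 1

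*Protocol*

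**What the plan says.** Protocol section 3 sets the evening out in order. Step 1 is "Arrive @ 17:00h with overnight bag". Step 2 is "Empty bladder and then provide and retain urine samples for the duration of the stay (assisted collection by researchers". The evening meal follows (step 3), and then "At 20:00h a research nurse will insert a cannula into a superficial arm vein" (step 4). Step 5 continues: "Further blood draws (5ml) will be taken at 22:00h, 2300h, 2400h,0100h and 0200h and the cannula withdrawn". Step 6 gives the product, placebo or supplement, at 22:00 on each day. Step 8 keeps the women nearby, "in close proximity to ensure 24h urine collection is complete", and step 9 reads "Repeat from 2 above to end of 2nd day".

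Protocol 4.i counts 32 urine samples of 24 h each, one per woman per day. Protocol 4.iii calls urinary PYD and DPD, normalised to creatinine, the best measure of the overall diurnal effect, and analyses them as the change over the 24 h after the product.

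The SAP hypothesis covers acute (0–4 h) and diurnal (24 h) turnover. Its TIME factor has levels 0, 1, 2, 3, 4 and 24 h, and urine DPD/creatinine is one of the dependent variables listed with it.

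No readable text gives an opening or closing void time for a pool, separates urine passed before 22:00, or provides a washout between the two products.

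**The concern.** The collection steps and the analysis run on different clocks. Collection starts at bladder emptying, in the early evening. The analysis in Protocol 4.iii starts at the product, at 22:00. A 24h pool that opens early must also close early, so the last hours after the product fall outside it.

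The products are 24 h apart, so in period 2 the misalignment does more than dilute the result. The urine passed between step 2 and 22:00 on the second evening falls in the last 2–5 h of the first product's 24 h, but is counted under the second product. In women given the supplement first, any late effect is lost from the supplement pool and added to the placebo pool. In women given placebo first, it is only lost. The understatement therefore depends on sequence. Normalising to creatinine does not correct assignment to the wrong product.

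If the voids are combined into the daily samples without a container change at 22:00, the two parts cannot be separated afterwards.

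**Working it through.** **Inputs.** Earliest opening of collection: 17:00 (step 1). Latest opening: 20:00 (step 4, the next clock time after step 2). Product: 22:00 on both days (step 6). Pool length: 24 h (step 8 and Protocol 4.i). Women: 16.

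**The plan's own count.** 16 women × 2 days = 32 pools, as stated.

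**Window.** Let L be the hours from opening to product.
- 17:00 opening: L = 22 − 17 = 5, so the pool runs from −5 to +19 h. Coverage is 19/24 = 79%.
- 20:00 opening: L = 22 − 20 = 2, so the pool runs from −2 to +22 h. Coverage is 22/24 = 92%.

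The first L hours of the period 2 pool are hours 19–24 (L = 5) or 22–24 (L = 2) after product 1.

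**SAP clock.** The step 5 draws at 22:00, 23:00, 24:00, 01:00 and 02:00 match SAP levels 0, 1, 2, 3 and 4 h. Time 0 is therefore the product, and 24 h is 22:00 the next evening. That is 2–5 h after a pool closing between 20:00 and 17:00.

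**Effect on the contrast.** Assumptions, none given in the documents: equal numbers in each sequence, near-constant creatinine excretion, and no supplement effect beyond 24 h. Let F(x) be the cumulative effect up to x hours after the supplement; the target is F(24).
- Placebo first: the supplement pool holds F(24−L) and the placebo pool holds none. Share retained = F(24−L)/F(24).
- Supplement first: the supplement pool holds F(24−L) and the placebo pool holds F(24) − F(24−L). Share retained = [2F(24−L) − F(24)]/F(24).

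*Constant effect for 24 h*, F(x) = x:
- L = 5: 19/24 = 0.792 and (38 − 24)/24 = 0.583; mean 0.6875.
- L = 2: 22/24 = 0.917 and (44 − 24)/24 = 0.833; mean 0.875.

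*Linear fade to zero at 24 h*, F(x) = x − x²/48, so F(24) = 12, F(19) = 11.48 and F(22) = 11.92:
- L = 5: 0.957 and 0.913; mean 0.935.
- L = 2: 0.993 and 0.986; mean 0.990.

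*Effect over by 24 − L hours:* F(24−L) = F(24), so 1.00 in both sequences.

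| Effect shape | 17:00 opening: placebo first / supplement first / mean | 20:00 opening: placebo first / supplement first / mean |
|---|---|---|
| Ends by +19 h (17:00) or +22 h (20:00) | 100% / 100% / 100% | 100% / 100% / 100% |
| Linear fade to 24 h | 96% / 91% / 93% | 99% / 99% / 99% |
| Constant for 24 h | 79% / 58% / 69% | 92% / 83% / 87.5% |

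**The case against.** The strongest objection is that the boundaries are inferred. Step 2 says when urine is kept, not how voids are divided into two samples, and it has no clock time of its own. The protocol says "Supplemenary Material contains a Flowchart", and that chart is not shown; it could set a 22:00 boundary. This stands as a limit on the finding. It does not supply a different reading of the numbered steps: any opening before 22:00 creates the mismatch, and the meal between step 2 and 20:00 makes a lead of more than 2 h likely.

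Second, the women may stay until 22:00 on the last evening. The steps list six draws per day, while Protocol 4.i counts seven, and the seventh could be the SAP's 24 h sample. Urine would then be available to +24 h, and the problem would be one of allocating voids between pools. That is fair. It makes the correction easier, but it does not put the pool boundary at 22:00.

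Third, one urine pool per day cannot have six TIME levels, so the SAP's 24 h entry may simply stand for the daily urine sample. This weakens the SAP as evidence of a closing time. The conflict between the collection steps and Protocol 4.iii does not depend on it.

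Fourth, the harm may be small. With a linear fade the average loss is 1–7%, and with an earlier end it is nil. An effect still strong at +19 h might also run past 24 h, where back-to-back products give a carry-over that no 22:00 boundary removes. Both points stand and bear on the size of the problem.

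Finally, the window as written covers one full clock cycle in both arms, which suits a diurnal measure. That is true, but part of the cycle is assigned to the wrong product.

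**Conclusion.** The concern holds on the readable text. Pools collected as the steps are written cover 19 to 22 of the 24 h after the product, and the period 2 pool takes in the last 2–5 h of product 1's 24 h. Coverage is incomplete, not absent.

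The average loss of the 24 h contrast lies between 0 and 31%. The top of that range needs both a 17:00 opening and an effect that stays constant for 24 h and then stops. If the effect ends before the pool closes, no contrast is lost, but the window is still mislabelled. The documents give no effect duration or shape, so the percentages illustrate a range and are not estimates.

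This should be fixed, because it affects a stated hypothesis and cannot be undone once voids are combined across 22:00. Confidence is medium: the flow chart may give the boundaries, step 9 restates no clock time for day 2, and the text does not say when voids are combined. No conflict with the length of stay is claimed.

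**What to change.** Add a timed void and a container change immediately before the 22:00 product on both evenings. Keep the pre-product urine out of the analysed pool, and state the opening and closing void times in both the protocol and the SAP. Product timing stays as it is. Then choose one of two closings:

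- **(a)** Close each pool at 22:00 the next day, matching the SAP's 24 h level, after confirming that attendance on the last evening allows it. This adds up to about 5 h on the last day if the women would otherwise leave at 17:00.
- **(b)** If they leave earlier, analyse the same shorter post-product window in both periods and report it by its actual hours, for example 0–19 h. This adds no stay, but leaves 17:00–22:00 unmeasured (5/24 = 21% of the day), so it is no longer a full diurnal measure.

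Do not use the period 2 pre-product urine as a baseline, since it falls within product 1's 24 h. If the flow chart already sets a 22:00 boundary, copy it into the numbered steps and the SAP.

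The direct cost is one extra void and container per evening, plus the wording. A 22:00 boundary does not remove carry-over from an effect lasting beyond 24 h.

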UNIVERSITY of LIMERICK

OLLS COIL LUIMNIGH

Statistical Plan

An evaluation of a Milk-Based Nutritional Supplement to Effect a Positive Change in Bone Health in Post-Menopausal Women at Risk of Osteoporosis.

Research Question or hypothesis:

Ho: Compared to a placebo control, ingestion of a milk protein-based supplement will not affect the temporal acute (0-4h) and diurnal (24h) rates of bone turnover in post-menopausal women with osteopenia.

Brief Background: In a novel approach to the timing of nutrient ingestion, the proposed nutrient intervention seeks to modify (reduce) the rate of bone resorption and promote the rate of bone formation to the benefit of bone health in post-menopausal women aged 50 to 70y diagnosed with osteopenia.

Study Design: A block randomised, crossover design

Participants: 16 post-menopausal women aged 50 to 70y diagnosed with osteopenia.

[figure not shown]
Statistical Analysis: ANOVA(R)

Independent variables:

TIME [6]
 0, 1, 2 3 4 and 24h

TEST PRODUCT [2]
 Placebo, MBPS

MODEL: Mixed model analysis of variance

Dependent variables

Bone Turnover [3]
 Blood CTX (bone resorption)
 Blood N1PD (bone formation)
 Urine DPD/Creatinine (bone resorption)

- a. Within-subject factor, **TIME (6)**
- b. Within-subject factor, **TEST PRODUCT (2)**
- c. Bonferroni corrected post-hoc comparisons

- i. Violation to normality (Shapiro – Wilk) data will be transformed by rank for analysis
- ii. Violation to homogeneity of variance-covariance matrices (Mauchly's W), e correction factors (Green-House Geisser, Huynh-Feld) will be applied
- iii. Violation to homogeneity of variance for post-hoc analysis (Levene's or Brown-Forsythe Test), Welsch-Satterthwaite corrections will be applied.

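### For serum CTX and P1NP, the SAP's TEST PRODUCT effect counts the 22:00 (0h) draw as an outcome level without baseline adjustment, and the SAP does not say which model term tests Ho

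*Protocol*

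**What the plan says.** Protocol section 3 (Procedures), step 4, at 20:00 once the cannula is in place: "a blood draw (5ml) will be taken and processed for later analysis". Step 5: "Further blood draws (5ml) will be taken at 22:00h, 2300h, 2400h,0100h and 0200h and the cannula withdrawn". Step 6 begins "At 22:00h consume", so the 0h draw and the intake share a clock time. Step 9 runs the second period on the following day: "Repeat from 2 above to end of 2nd day".

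Protocol section 4.i: "In total 224 (16 subjects * 7 samples * 2 d) blood samples will be collected". Section 4.ii asks for two things from a repeated measures ANOVA of the serum markers: "The magnitude and time course of the acute response (0-4h) change in bone turnover".

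The SAP has two within-subject factors, TIME (six levels: 0, 1, 2, 3, 4 and 24h) and TEST PRODUCT (two levels), in a mixed model ANOVA, followed by "Bonferroni corrected post-hoc comparisons". Its readable text lists no baseline covariate, change score or period term. It names neither the interaction nor any contrast with 0h, and links no term to Ho. Ho itself covers both the acute 0-4h and the 24h rates.

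**The concern.** In this factorial model the natural answer to the question of magnitude is the TEST PRODUCT effect, averaged over the TIME levels. One of those levels is 0h, when the product cannot yet have acted. Averaging it in shrinks the estimated effect. With no baseline term, each woman's difference in starting level between the two nights also stays in the error.

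TIME x PRODUCT answers the question of time course and uses 0h implicitly as its reference, so it is free of this fault. The two terms suit different response shapes and can disagree. With 16 subjects, judging Ho on the PRODUCT effect could miss a sustained 1-4h effect although the baseline that would sharpen the test has been collected. Judging it on whichever term is significant would not hold the error rate at 5%.

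**Working it through.** **1. Matching draws to TIME levels.** Relative to the 22:00 intake, the listed draws fall at -2, 0, 1, 2, 3 and 4h. No draw is listed at 21:00, so only 22:00 fits as 0h. The protocol's total reproduces: 16 x 7 x 2 = 224. The listed clock times give six draws a night, 16 x 6 x 2 = 192; the seventh is presumably the SAP's 24h level. The SAP's six levels also use 192, and the remaining 224 - 192 = 32 samples match the 20:00 draw.

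**2. Dilution.** The PRODUCT effect is the mean of the effects at the levels included. For an effect of size d at each of 1-4h and zero at 0h:
- levels 0-4h: 4d/5 = 0.80d
- six levels, gone by 24h: 4d/6 = 0.67d
- six levels, persisting at 24h: 5d/6 = 0.83d

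**3. Error variance.** The documents give no SD or response shape, so all that follows is assumed: log scale, residual SD r = 0.08, between-night SD b = 0.05 or 0.10, and an 8% reduction, d = |ln 0.92| = 0.083. The period shift is left out of this step.
- Paired difference, mean of 0-4h: variance 2(b² + r²/5). At b = 0.05: 2(0.0025 + 0.00128) = 0.00756, SD 0.087. At b = 0.10: 2(0.0100 + 0.00128) = 0.02256, SD 0.150.
- Paired difference, mean of 1-4h adjusted for 22:00: variance 2[b² + r²/4 - b⁴/(b² + r²)]. At b = 0.05: 2(0.0025 + 0.0016 - 0.00070) = 0.0068, SD 0.082. At b = 0.10: 2(0.0100 + 0.0016 - 0.0061) = 0.0110, SD 0.105.

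The standardised effect for the PRODUCT term is 0.8 x 0.083 = 0.066 over its SD: 0.76 and 0.44. For the adjusted contrast it is 0.083 over its SD: 1.01 and 0.79.

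**4. Power by simulation.** Two-period crossover, 8 per sequence, period shift 0.03, two-sided 5%, 6,000 trials per setting. PRODUCT effect: paired t on the mean of 0-4h. Interaction: Greenhouse-Geisser F over 0-4h. Adjusted contrast: within-subject 1-4h difference regressed on the 22:00 difference and sequence, test of the intercept, 13 df.

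| Effect | Residual SD | PRODUCT effect (b = 0.05 / 0.10) | TIME x PRODUCT | Adjusted 1-4h mean (b = 0.05 / 0.10) |
|---|---|---|---|---|
| Flat 8%, 1-4h | 0.08 | 78% / 37% | about 45% | about 95% / 80% |
| Flat 8%, 1-4h | 0.05 | not tabulated | about 90% | 97-99% across both |
| 8% at 1-2h only | 0.08 | 26% / 13% | 66% / 64% | 44% / 30% |

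Between-night SD cancels from the interaction, so residual SD alone drives its power: at 0.06 it is about 73% for the flat effect.

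**5. Source of the gain (flat effect, residual SD 0.08).** At b = 0.05, dropping 0h takes 78% to about 92%, the period term to about 93%, and the covariate to about 95%. At b = 0.10 the covariate matters most, taking about 53% to about 81%.

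**6. Type I error.** The adjusted contrast holds about 5%. Rejecting Ho if either PRODUCT or TIME x PRODUCT is significant gives about 7-8% per marker.

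**The case against.** The strongest reply is that a repeated measures ANOVA yields TIME x PRODUCT as standard, that Ho and Protocol section 4.ii both speak of the time pattern, and that 0h belongs in the model as the reference for that interaction. This stands. A reader might infer that the SAP tests Ho on the diluted PRODUCT effect; the documents do not say so. Keeping 0h as a level is not wrong in itself, and the loss applies only if the PRODUCT effect is used to answer the question of magnitude.

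A reader might also infer that the interaction is weak, or that the adjusted contrast is always better. Neither is supported. Interaction power for a flat effect runs from about 45% to about 90% over residual SDs of 0.08 to 0.05. It beats the adjusted contrast for a short 1-2h effect, and for suppression followed by a half-size rebound (93% against 15% or 11%).

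Baseline adjustment can also import carry-over, because the day-2 22:00 draw falls 24h after the day-1 product. If a quarter of the effect carried into the day-2 baseline only, the adjusted estimate would shift by -0.003 to -0.006 against a true -0.083, and the unadjusted estimate not at all. If it carried through all of night 2, the shifts would be +0.004 to +0.008 adjusted and +0.010 unadjusted. The 0h-referenced interaction already rests on the same assumption of a clean baseline.

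The 20:00 draw is not evidence of an error. The step 4 wording describes laboratory handling, and the flow charts are not shown. In the readable text it has no statistical role, which is a gap in detail only. The order of draw and intake at 22:00 is implied by steps 5 and 6 and needs only a sentence. Finally, the Bonferroni rule is stated for post-hoc comparisons; it does not settle which omnibus term decides Ho.

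**Conclusion.** The point holds for serum CTX and P1NP (which the SAP's formation marker is taken to be). Urine has one value per subject per day, so no 0h level enters there. As specified, the PRODUCT effect includes a level at which the product cannot have acted, leaving 4/5 of a flat effect over 0-4h and 4/6 or 5/6 over six levels, and it makes no use of the 22:00 baseline. That much is arithmetic, given that the 0h draw precedes intake. The size of the power loss is not fixed by the documents. It depends on the assumed residual and between-night SDs and on response shape, and much of the gain at the smaller between-night SD comes from dropping 0h rather than from the covariate. TIME x PRODUCT is sound for the time course. What is missing is a statement of which term decides Ho. The dilution is a loss of sensitivity and does not raise the false-positive rate; that rises only if Ho is rejected on either of two unranked terms.

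**What to change.** For CTX and P1NP, amend the SAP before the data are examined:

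- Estimate the PRODUCT effect from the post-intake values (mean or AUC of 1-4h). Use that night's 22:00 value as covariate, entered as the within-subject difference between nights, with a period term. Do not count 0h as an outcome level in this estimate.
- Keep TIME x PRODUCT over 0-4h, with 0h included, as the test of time course.
- State which of the two is primary for Ho, and the alpha rule if both can reject it.
- Report the estimate without the covariate as a sensitivity analysis for carry-over.
- As clarifications only, state the statistical use (if any) of the 20:00 sample, and that the 22:00 draw precedes intake if that is intended.
- Show any supporting power figures over a range of residual SD as well as between-night SD.

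The cost is wording and about 2 df (15 to 13), with no new samples. The adjustment assumes little carry-over of the day-1 product into the day-2 22:00 value, which is why the unadjusted estimate should sit beside it.

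### Standardised main meals before the 22:00h intake number one in period 1 and four in period 2, which can add avoidable within-woman noise but does not bias the product comparison

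*Protocol*

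**What the plan says.** Protocol section 3 (Procedures) sets out one continuous stay: "Subjects will attend for a 2 day overnight residence". Step 1 reads "Arrive @ 17:00h with overnight bag". Urine collection opens at step 2. Step 3 is "Consume a standardised evening meal (pre-prepared by the research dietitian", with no clock time. The product is taken at 22:00h (step 6), with blood draws from 20:00h to 02:00h (steps 4 and 5). Breakfast and lunch appear only at step 8: "Consume a standardised breakfast and lunch (pre-prepared by the research dietitian) whilst living in and around the University grounds". Step 9 is "Repeat from 2 above to end of 2nd day", so period 2 begins at urine collection with no new arrival.

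The only dietary step before the stay is at screening: "dietary intake of calcium and Vit D (by food frequency questionnaire, 1h) will precede the experimental protocol". That assesses intake of two nutrients; it is not a run-in or a controlled diet.

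The Protocol describes "A block randomised, cross-over design of 24h rates of bone turnover", and the SAP gives the sample as "16 post-menopausal women aged 50 to 70y diagnosed with osteopenia". The SAP model lists TIME (0, 1, 2, 3, 4 and 24h) and TEST PRODUCT as within-subject factors, with no period or sequence term.

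**The concern.** The protocol treats diet as relevant to the outcome: a dietitian prepares the main meals in residence, and calcium and vitamin D intake are screened. Yet the breakfast and lunch before the intake are specified in only one of the two periods. If arrival-day eating varies from woman to woman and affects bone turnover that evening, each woman's period 1 values carry an extra random component that her period 2 values do not.

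What is at stake is precision. With 16 women, the crossover depends on a small within-woman error, and the documents give no power calculation showing how much extra variance the trial can absorb. A period term removes an average difference between day 1 and day 2, but not a component that differs between women.

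**Working it through.** There is no stated figure to reproduce, since neither document gives a variance, effect size, alpha or power.

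**1. Schedule trace (Protocol section 3, steps 1 to 9)**

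| Standardised main meals so far | Period 1 | Period 2 |
|---|---|---|
| Before urine collection opens (step 2) | 0 | 3 (day 1 evening meal, breakfast, lunch) |
| Before the 22:00h intake (step 6) | 1 (evening meal) | 4 (the three above plus day 2 evening meal) |
| Within the 24h urine collection | evening meal, breakfast, lunch | evening meal, breakfast, lunch |

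The first two rows differ between periods; the third matches.

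**2. Is the product contrast biased?** Write each woman's product difference as d = tau + pi in one order and tau - pi in the other, where tau is the product effect and pi the average period effect. The mean of d over n1 and n2 women is tau + pi(n1 - n2)/16.

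- 8:8 gives tau, so no bias.
- 9:7 gives tau + 0.125 pi and 10:6 gives tau + 0.25 pi. Simulation at pi = 1 (40,000 runs) gave 0.126 and 0.250. A period term removes this.

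The imbalance would arise only by chance or through dropout, and would not be specific to diet. Omitting the period term also costs power. With tau = 0.75 SD of the difference, an 8:8 split and two-sided 0.05, simulated power without the term is 80%, 78%, 72% and 49% for pi = 0, 0.25, 0.5 and 1 SD, against about 80% throughout with it. That is a modelling matter, separate from the noise sized next.

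**3. Noise that a period term leaves behind.** Assume a within-woman SD of s in each period, and that variation in arrival-day intake adds an independent SD of k*s in period 1 only.

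- Variance of the within-woman difference: s^2 + s^2(1 + k^2) = (2 + k^2)s^2, against 2s^2 without it.
- SE ratio = sqrt((2 + k^2)/2). Effective n = 16 / ((2 + k^2)/2).
- Power is for the same assumed effect (0.75 SD of the difference at k = 0), two-sided 0.05, period term fitted (df 14).

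| k (assumed) | (2 + k^2)/2 | SE ratio | Effective n | Power |
|---|---|---|---|---|
| 0 | 1 | 1.000 | 16 | about 80% |
| 0.25 | 1.03125 | 1.016 | 15.5 | about 78% |
| 0.5 | 1.125 | 1.061 | 14.2 | about 75% |
| 1 | 1.5 | 1.225 | 10.7 | about 63% |

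k = 1 means that arrival-day diet alone doubles the period 1 variance. Nothing in the documents supports a value that large; it is shown as an extreme.

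**4. Where k is likely to be small.** The acute analysis concerns change over 0-4h, and TIME has a 0h level. A dietary shift that moves all of an evening's serum values equally cancels from a woman's change from her own 0h value; only a shift that alters the shape of the 0-4h curve remains. For 24h urine, the specified meals within both collections match, so only diet before collection opens can differ.

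**The case against.** The strongest objection is that the plan already controls what lies closest to the outcome. Any food eaten before arrival is at least 5 hours before the intake (17:00h to 22:00h), with a standardised meal in between. The 0h value absorbs a constant serum shift, and meals within the urine collections already match. This stands, and it makes the lower end of the range more plausible than the upper end.

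Two descriptions are tempting but go too far. A reader might infer that women eat freely before arrival; the text is merely silent, and a pre-arrival instruction in the flowchart cannot be excluded. A reader might also call the second day fully standardised; main meals are supplied, but snacks, drinks and activity on the grounds are not described.

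A reader might also infer that product and prior diet are confounded. The documents do not support that. Diet before the first intake cannot depend on a randomly assigned order, and an average period difference cancels when the two orders are balanced.

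Against the objection, the unequal schedule itself is plain in the steps, and neither randomised order nor a period term removes variation that differs from woman to woman.

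**Conclusion.** The point holds as a limited one about precision. The readable text standardises main meals unequally before the two intakes (one against four) and before the two urine collections (none against three). This can add within-woman noise in period 1. It does not bias the product contrast.

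The size is unknown. Under the assumed model the loss runs from negligible (k = 0.25, equivalent to half a woman out of 16) to material (k = 1, about five women). The documents give no basis for choosing k, and a reader should not infer that a loss of several women is expected. The conclusion also rests on there being no pre-arrival meal rule in the figure that is not shown. The trial stays interpretable either way; the case for acting is that the remedy is cheap.

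**What to change.** If a rule on eating before arrival already exists, state it in Protocol section 3. If not:

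- Give each woman the same pre-prepared breakfast and lunch used in step 8, to eat on the arrival day before 17:00h, with a short intake log.
- Give step 3 a clock time and serve the evening meal at that time on both evenings.

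The cost is 16 x 2 = 32 extra meals from the dietitian who already prepares them, plus getting them to the women; the protocol gives no interval between screening and the stay, so delivery may need arranging. Adherence at home will be imperfect, and the log records this without verifying it. No extra procedure or staff is needed.

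This does not remove other differences between the periods, such as the preceding night of blood draws until 02:00h. Adding period and sequence to the SAP model would deal with the average part of those differences and is worth doing in its own right, but it does not replace the meals.
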